2. BACKGROUND

2.1 Follicular Lymphoma (FL)

There will be approximately 70,000 new cases of non-Hodgkin lymphoma (NHL) this year in the United States, and 20,000 deaths. Follicular lymphoma is the second most common B cell NHL, with approximately 25,000 new cases diagnosed each year in the United States. It is the most common indolent B cell NHL and generally presents at advanced stage and is incurable with conventional therapies. Though incurable, it does tend to be chemotherapy responsive with high rates of initial response, but it exhibits progressively lower rates of response and remission duration with subsequent lines of therapy, and always with invariable relapse.

Of the many effective treatment modalities for FL, overall survival benefits have not been demonstrated favoring one treatment approach over another, with the exception of rituximabcontaining chemotherapy versus chemotherapy alone.^{4,5} Increased intensity regimens have been shown to improve CR rates and PFS without improvement in OS. Choice of therapy has thus been based upon balancing efficacy and tolerability. Available treatment approaches currently employed in chemotherapy naïve patients include rituximab monotherapy, R-bendamustine, R-CVP (rituximab, cyclophosphamide, vincristine, prednisone), and R-CHOP (rituximab, cyclophosphamide, adriamycin, vincristine, prednisone). For the relapsed/refractory setting, these options remain but additional options include fludarabine-based regimens, radioimmunotherapy, and targeted therapies with the immunomodulatory drug lenalidomide and the PI3 kinase inhibitor idelalisib.^{6,7} Furthermore, lenalidomide has been used in combination with rituximab in the upfront setting and has excellent response rates, including a CR rate of 87%.⁸

Both autologous and allogeneic stem cell transplantation have been used for the treatment relapsed FL.^{9,10} The former may consolidate a second or third line chemotherapy remission and results in a median progression free survival (PFS) of 4-5 years. The latter is currently the only potentially curative therapy for advanced stage FL, with a long term PFS of 60-80%, but with a considerable risk of morbidity and mortality. It is thus reserved for multiply relapsed disease with suboptimal depth and/or duration of response. Its efficacy, however, supports the use of immune strategies for the treatment of this disease.

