3. PARTICIPANT SELECTION

3.1 Eligibility Criteria

Participants must meet the following criteria on screening examination to be eligible to participate in the study:

- 3.1.1 Patients must have histologically determined follicular lymphoma, grade 1-3A, with pathologic review at the participating institutions, that has either:
 - Relapsed or primary refractory after at least one line of therapy including anti-CD-20 monoclonal antibody treatment (part A) or;
 - Has had no previous anti-lymphoma therapy other than corticosteroids or radiotherapy (part B).
- 3.1.2 Patients with active histologic transformation are excluded. Relapsed/refractory patients with prior transformation may be included as long as there is no evidence of transformation at the time of study entry by pathology, imaging, or clinical status
- 3.1.3 Patients in part B, without prior anti-lymphoma therapy, must be in need of treatment as defined by any of the following criteria:
 - Symptomatic adenopathy
 - Organ function impairment due to disease involvement, including cytopenias due to marrow involvement (WBC <1.5x10⁹/L; absolute neutrophil count [ANC] <1.0x10⁹/L, Hgb <10g/dL; platelets <100x10⁹/L)
 - Constitutional symptoms
 - Maximum diameter of disease \geq 7cm
 - ≥ 3 nodal sites of involvement
 - Risk of local compressive symptoms
 - Splenomegaly (craniocaudal diameter \geq 16cm on CT imaging)
 - Clinically significant pleural or peritoneal effusion
 - Leukemic phase (> $5x10^{9}/L$ circulating malignant cells)
 - Rapid generalized disease progression
 - Renal infiltration
 - Bone lesions
- 3.1.4 Patients may have had a prior autologous stem cell transplant and may have been treated with autologous chimeric antigen receptor T-cells (CAR T-cells).
- 3.1.5 Not in need of urgent cytoreductive therapy in the opinion of the investigator

- 3.1.6 Measurable disease that has not been previously irradiated on CT scans of at least 1.5 cm, OR if the patient has had previous radiation to the marker lesion(s), there must be evidence of progression since the radiation. Imaging must be completed no greater than 6 weeks prior to study enrollment.
- 3.1.7 Eastern Cooperative Oncology Group (ECOG) performance status 0-2 (see Appendix A)
- 3.1.8 Adequate hematologic and organ function:
 - Absolute neutrophil count $\geq 1.0 \times 10^{9}$ /L unless due to marrow involvement by lymphoma in which case ANC must be $> 0.5 \times 10^{9}$ /L

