5. TREATMENT PLAN

5.1 Study Design

This study will consist of 3 cohorts (A1-A3) in the relapsed/refractory setting tested in two stages: 1) dose escalation and 2) dose expansion. If a combination meets prespecified safety and efficacy endpoints in the expansion stage, and after discussion with regulatory authorities, 2 additional cohorts (B1, B2) will open testing these combinations in the upfront setting in previously untreated FL patients.

The cohorts for this study will be as follows:

	Dose escalation	0	T T/ •1 1		DE 04510600
		Rituximab (or rituximab	Utomilumab	Avelumab	PF-04518600
		biosimilar)			
t A1a	Dose Level 1	375mg/m2 IV q7d for 4 doses (cycle 1 only)	100mg IV q28d cycle 1-6	3mg/kg IV q14d cycle 1-6	n/a
Cohort A1a	Dose Level 2	375mg/m2 IV q7d for 4 doses (cycle 1 only)	100mg IV q28d cycle 1-6	10mg/kg IV q14d cycle 1-6	n/a
	Dose Level 0	n/a	n/a	n/a	0.3mg/kg IV q14d cycle 1-6
Cohort A2a	Dose Level 1	375mg/m2 IV q7d for 4 doses (cycle 1 only)	n/a	n/a	0.3mg/kg IV q14d cycle 1-6
Co	Dose Level 2	375mg/m2 IV q7d for 4 doses (cycle 1 only)	100mg IV q28d cycle 1-6	n/a	0.3mg/kg IV q14d cycle 1-6
Cohort A3a	Dose Level 1	375mg/m2 IV q7d for 4 doses (cycle 1 only)	n/a	3mg/kg IV q14d cycle 1-6	0.3mg/kg IV q14d cycle 1-6
Cohoi	Dose Level 2	375mg/m2 IV q7d for 4 doses (cycle 1 only)	n/a	10mg/kg IV q14d cycle 1-6	0.3mg/kg IV q14d cycle 1-6

• Dose escalation stage:

- Dose Expansion Cohorts
 - Cohort A1b: Rituximab (or rituximab biosimilar), utomilumab, avelumab at the recommended phase 2 dose
 - Cohort A2b: Rituximab (or rituximab biosimilar), utomilumab, PF-04518600 at the recommended phase 2 dose
 - Cohort A3b: Rituximab (or rituximab biosimilar), avelumab, PF04516800 at the recommended phase 2 dose
- Upfront Cohorts (B1, B2) (n=up to 15)
 - Cohort B1: Rituximab (or rituximab biosimilar), utomilumab, avelumab at the recommended phase 2 dose
 - Cohort B2: Rituximab (or rituximab biosimilar), utomilumab, PF-04518600 at the recommended phase 2 dose

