The anti-tumor activity of single agent utomilumab in patients with advanced malignancies and utomilumab in combination with rituximab in patients with B-cell NHL is being assessed in Study B1641001. This study does not have a control arm, and tumor responses are reported by Investigators per Response Evaluation Criteria in Solid Tumors (RECIST 1.1)⁴² for Portion A patients or International Working Group (IWG) criteria⁴³ for Portion B. Forty-seven patients in Portion A and 40 patients in Portion B (24 male, 16 female, mean age 60.8 years) have been treated.

In the single-agent portion (Portion A) of the study, best objective responses observed have been 1 CR and 1 PR in Merkel cell carcinoma (MCC) patients who were treated at 0.24 mg/kg and 0.6 mg/kg, respectively.

In patients treated with the combination of utomilumab and rituximab (Portion B), 8 patients with follicular lymphoma (7 patients were refractory to prior rituximab-containing regimen) achieved an objective response: 4 patients achieved a CR (2 treated at 1.2 mg/kg, 1 at 0.12 mg/kg, and 1 at 0.03 mg/kg) and 4 patients achieved a PR (2 treated at treated at 0.18 mg/kg, 1 treated at 1.2 mg/kg, and 1 treated at 5.0 mg/kg). One (1) patient with CD20 + Hodgkin's lymphoma treated at 1.2 mg/kg achieved a PR and 1 patient with Mantle Cell Lymphoma (MCL) treated at 2.4 mg/kg achieved a PR.

8.1.1.6 *Ordering*

Utomilumab will be supplied by Pfizer. No patients or third-party payers will be charged. Use the Drug Supply Request Form provided to order utomilumab. For all inquiries regarding utomilumab supplies, please contact:

[name] [name] [contact]

Utomilumab is a sterile, colorless solution intended for IV administration. The drug product provided will contain 100mg of utomilumab in a 10mL solution in single-use glass vials, stoppered with a rubber septum and sealed with an aluminum polypropylene flip-off seal.

Packaging and labeling will be in accordance with applicable local regulatory requirements and applicable Good Manufacturing Practice (GMP) guidelines.

Utomilumab will be packed in cartons each containing one vial. The information on the labels will be in accordance with approved submission documents. Utomilumab will be shipped in transport cool containers (2°C to 8°C) that are monitored with temperature monitoring devices.

8.1.1.7 *Preparing and Dispensing*

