8.2 Other Agent(s)

8.2.1 Rituximab

Single agent monoclonal antibodies are an attractive treatment option given excellent tolerability. Rituximab is approved as a single agent in relapsed or refractory FL and in combination with chemotherapy for first line therapy of FL.⁵¹

Rituximab is a genetically engineered, chimeric, murine/human monoclonal antibody directed against the CD20 antigen found on the surface of normal and malignant pre-B and mature B cells. The antibody is an IgG1 κ immunoglobulin containing murine light and heavy-chain

variable region sequences and human constant region sequences. Rituximab is composed of two heavy chains of 451 amino acids and two light chains of 213 amino acids (based on cDNA analysis) and has an approximate molecular mass of 145 kD. Rituximab has a binding affinity for the CD20 antigen of ~8.0 nM. Several mechanisms of action have been proposed in various models including complement-dependent cytotoxicity (CDC), antibody-dependent cell-mediated cytoxicity (ADCC), induction of apoptosis, and a "vaccinal" effect.⁵² It is likely that rituximab works through a combination of these mechanisms.

The objective response rate for rituximab monotherapy in relapsed low-grade B-cell lymphoma is approximately 24-36% with complete response rates of approximately 7%.⁵³ Several mechanisms for rituximab resistance have been proposed including variable CD20 expression by lymphoma subtype, variability in complement activation, and polymorphisms in Fc receptors.⁵⁴⁻⁵⁶ Novel agents that overcome these resistance mechanisms might offer similar complete response rates to combined chemotherapy and immunotherapy with improved tolerability.

Rituximab monotherapy has been evaluated in the upfront therapy as well. When given as 4 weekly infusions to patients who would otherwise have undergone observation, the objective response rate was 72% and the median time to progression was 2.2 years.⁵¹ The addition of maintenance rituximab, given once every 8 weeks for 4 treatments, to patients with at least stable disease following induction therapy with rituximab monotherapy is associated with an improvement in event free survival (24 versus 13 months, <0.001).⁵⁷

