11. MEASUREMENT OF EFFECT

11.1 Disease Response Assessments

18F-fluorodeoxyglucose (18F-FDG) Positron Emission Tomography (PET) imaging will be used in conjunction with Computerized Tomography (CT) imaging to confirm a disease assessment of CR at the end of treatment. The screening 18F-FDG PET-CT imaging will be used to determine evaluable index lesions for each patient. For 18F-FDG PET-CT, tumor background ratios and development of new sites of abnormality will be recorded.

Results of the 18F-FDG PET studies will be scored according to methods developed by the American College of Radiology Imaging Network. All centers participating in the study will use the same 18F-FDG PET methodologies and measures, to the extent possible, and one center will be designated as the central lab to be used for final interpretation of 18F-FDG PET data.

Anti-cancer activity will be assessed at baseline, during treatment as specified in the Study Calendar, whenever disease progression is suspected (eg, symptomatic deterioration), at the time of withdrawal from treatment (if not performed in the previous 6 weeks) or at the end of treatment (4-6 weeks from the last dose of study therapy) and at follow-up visits 6, 12, and 18 months (+/- 2weeks) from the end of therapy or until disease progression.

If imaging is used in disease assessment, the same imaging technique (CT) used to characterize each identified and reported lesion at baseline will be employed in post-baseline disease assessments.

Assessment of response will be made using the Lugano 2014 criteria and LyRIC (Appendix D).

All patients' files and radiologic images and pathology samples must be available for source verification and for potential peer review.

For all patients who achieve a complete response (CR) by imaging, a bone marrow biopsy is necessary to confirm a complete remission.

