13.2 Sample Size, Accrual Rate and Study Duration

13.2.1 Determining RP2D

The Dose Escalation phase of this study follows a 3+3 design with 2 or 3 dose levels for each cohort to determine the RP2D for each drug combination being tested. The RP2D will be defined as the highest dose level for which there are no more than 1/6 DLTs observed.

The following table shows the probability of escalation under various true DLT rates. With this design there is 91% probability of dose escalation if the true rate of DLT is 10% and 8% probability of escalation if the true DLT rate is 60%.

True Rate of DLT	Probability of escalation
10%	0.91
20%	0.71
30%	0.49
40%	0.31
50%	0.17
60%	0.08

Dose Expansion

Once the RP2D is established for a given cohort/drug combination in the relapsed/refractory setting (part A), an additional 9 or 12 eligible patients will be treated at the RP2D, for a total of 15 patients treated at that dose level. Whether it is 9 or 12 is dependent on whether 6 or 3 patients were treated at that dose level to determine the RP2D, respectively. With 15 patients, the 90% confidence interval for DLT will be no wider than +/-23%.

A combination will be judged promising in terms of efficacy **in part A (relapsed/refractory setting)** if in addition to being tolerable 3 or more patients out of 15 obtain a CR (based on a null hypothesis of CRR 5% and alternative hypothesis of CRR 30% with 87% power and a 4% one sided type I error).

True but unknown CR rate	0.05	0.1	0.15	0.2	0.25	0.3
Prob of observing ≥ 3 CRs	0.04	0.18	0.40	0.60	0.76	0.87

In the **relapsed/refractory setting (part A)**, a particular combination (A1b, A2b, A3b) will be judged tolerably safe if 3 or fewer patients out of 15 experience a DLT (based on a null hypothesis for DLT rate of 40% and an alternative hypothesis of 10% with 94% power and a 9% one-sided type I error).

True but unknown prob. of excessive toxicity	0.05	0.1	0.15	0.2	0.25	0.3	0.35	0.4
Prob of observing ≤3 pts with excessive tox	0.99	0.94	0.82	0.65	0.46	0.30	0.15	0.09

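### Is the 4% type I error of the Part A efficacy rule understated because its 5% null lies below the CR rate of about 7% cited for rituximab alone?

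*Combined protocol and SAP*

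**What the plan says.** Section 13.2.1 (Dose Expansion) sets the Part A efficacy rule at 3 or more CRs among 15 patients, on top of tolerability. It gives the basis as "null hypothesis of CRR 5% and alternative hypothesis of CRR 30% with 87% power and a 4% one sided type I error". The table below it lists the probability of passing at true CR rates of 0.05, 0.10, 0.15, 0.20, 0.25 and 0.30 as 0.04, 0.18, 0.40, 0.60, 0.76 and 0.87.

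Rituximab is part of every expansion regimen in Section 5.1, for example "Cohort A1b: Rituximab (or rituximab biosimilar), utomilumab, avelumab at the recommended phase 2 dose"; A2b and A3b contain it too. In Section 8.2.1 the response figures are for "rituximab monotherapy in relapsed low-grade B-cell lymphoma is approximately 24-36% with complete response rates of approximately 7" per cent.

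Section 3.1.1 defines the Part A population: "Relapsed or primary refractory after at least one line of therapy including anti-CD-20 monoclonal antibody treatment". Section 11.1 adds a condition to the endpoint: "For all patients who achieve a complete response (CR) by imaging, a bone marrow biopsy is necessary to confirm a complete remission".

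**The concern.** In a single-arm screen of rituximab plus new agents, the natural false pass is a combination that adds nothing to rituximab. Read that way, the null should be the CR rate of rituximab alone. The only such figure the protocol gives for relapsed disease is about 7%. Section 13.2.1 uses 5%, gives no reason for going lower, and prints no value at 7%.

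The rule also has consequences. It is the efficacy half of calling a combination promising. For A1b and A2b it is one of the conditions for treating previously untreated patients. If 7% were the right null, the reported 4% would be less than half of the real false-pass probability.

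**Working it through.** **Inputs.** n = 15, pass if X ≥ 3, null 5%, alternative 30% (all Section 13.2.1). Reference CR rate of about 7% (Section 8.2.1).

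**Formula.** With X binomial(15, p), P(X ≥ 3) = 1 − P(0) − P(1) − P(2).

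**Step 1: the plan's own figures.**
- p = 0.05: the three terms are 0.4633, 0.3658 and 0.1348. P(X ≥ 3) = 0.0362 at full precision, stated as 4%.
- p = 0.30: the terms are 0.0047, 0.0305 and 0.0916. P(X ≥ 3) = 0.8732, stated as 87%.
- The other table entries come out as 0.1841, 0.3958, 0.6020 and 0.7639, and match the printed 0.18, 0.40, 0.60 and 0.76.

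The plan's arithmetic is right throughout.

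**Step 2: the value at 7%.** 1 − (0.3367 + 0.3801 + 0.2003) = 0.0829. The difference from 5% is 0.0829 − 0.0362 = 0.0467, or 4.7 percentage points. In expected CRs it is 15 × 0.05 = 0.75 against 15 × 0.07 = 1.05.

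**Step 3: both directions.** The 7% is approximate, and a rate below 5% is also possible in pretreated patients, so the range should run both ways.

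| True CR rate | P(≥3 of 15) |
|---|---|
| 3% | 0.009 |
| 4% | 0.020 |
| 5% | 0.036 |
| 6% | 0.057 |
| 7% | 0.083 |
| 8% | 0.113 |
| 10% | 0.184 |

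The printed table contains the 5% and 10% rows, so 7% falls inside a bracket the reader can already see.

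**Step 4: does the 7% figure carry over to Part A?** Set side by side:
- Section 8.2.1 describes relapsed low-grade B-cell lymphoma in general. It gives neither the prior rituximab exposure nor the CR definition behind the 7%.
- Part A takes follicular lymphoma only, after treatment that included an anti-CD20 antibody, and admits primary refractory disease (Section 3.1.1).
- Section 2.1 says of follicular lymphoma that "it exhibits progressively lower rates of response and remission duration with subsequent lines of therapy".
- Part A counts an imaging CR only after marrow confirmation (Section 11.1).

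Prior anti-CD20 treatment, refractory disease and marrow confirmation would each tend to push a rituximab-alone CR rate down. None of them fixes it at 5%, but together they make a null below 7% defensible.

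**Step 5: what a pass leads to.** Tolerability (3 or fewer DLTs of 15) is also required. P(DLT ≤ 3) is 0.9444 at a 10% DLT rate and 0.6482 at 20%. With independence assumed, the joint pass probability at a 7% CR rate is 0.0829 × 0.9444 = 0.078, or 0.0829 × 0.6482 = 0.054. Part B then opens only if the criteria are met, "and after discussion with regulatory authorities, 2 additional cohorts (B1, B2) will open". Each Part B cohort has its own test (6 or more CRs of 15) and its own DLT stopping rule.

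**Step 6: would another null lead to another rule?** Requiring 4 or more CRs gives 0.018 at 7% but reduces power at 30% from 0.87 to 0.70. For a small screen that is a poor exchange, so 3 of 15 is a reasonable rule under either null.

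**The case for a change.** The strongest opposing case is that the protocol names only one CR rate for rituximab alone in relapsed disease, and Section 13.2.1 neither uses it nor says why. The pass probability exceeds 5% once the true CR rate passes 5.7%, so the nominal error depends on that choice. The population argument for 5% is one that a reader has to assemble, because the protocol does not make it. The protocol's own data could also be read as arguing against a low null. In the earlier utomilumab-plus-rituximab study, Section 8.1.1.5 reports that "8 patients with follicular lymphoma (7 patients were refractory to prior rituximab-containing regimen) achieved an objective response: 4 patients achieved a CR".

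Part of this stands. The rationale for 5% is absent, and a sentence giving it would have been helpful. The utomilumab data, however, do not bear on the point. They come from a combination with an active partner, over mixed doses, under different response criteria, with 40 treated patients of all histologies and no follicular denominator. They cannot show what rituximab alone would achieve in Part A. What remains is a wish for one more table column and a line of explanation. Neither would alter a decision or a result.

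**Conclusion.** The concern does not hold. The 4% is correct, is stated for a named null of 5%, and stands beside a table that shows how fast the pass probability rises above it. The figure of 8% at a CR rate of 7% is also correct, but it is the error rate of a different null, one the protocol does not adopt and whose source population is not that of Part A. Reasonable statisticians could choose either value.

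The size of the matter is 4.7 percentage points on the efficacy rule alone. The joint pass probability at 7% is 5.4% to 7.8% once tolerability is included, if DLT rates are 10% to 20% and DLT and CR are independent. That is tolerable for a phase 1b screen with further checks behind it. The sample size, the threshold of 3 CRs and the 87% power at 30% are the same under either null. The conclusion rests on taking the 7% for what the protocol says it is: an approximate rate in relapsed low-grade B-cell lymphoma, not an expected rate for this trial's patients.

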NCI Protocol #: N/A

DF/HCC Protocol #: 18-311

TITLE: A Multi-Cohort Phase 1b Clinical Trial of Rituximab in Combination with Immunotherapy in Untreated and Previously Treated Follicular Lymphoma

Coordinating Center:	Dana-Farber Cancer Institute
*Principal Investigator (PI):	[name] Dana-Farber Cancer Institute [name] (p): [contact] (f): [contact] [contact]
Other Investigators:	DFCI: [name], PhD; [name]; [name]; [name]; [name]; [name], PhD; [name]; [name]; [name], PhD; [name]; [name]; [name]; [name], PhD; [name], PhD; [name], NP; [name], APRN; [name], NP; [name], PA-C; [name], DNP City of Hope: [name] Emory: [name] University of Chicago: [name] Washington University: [name] Yale University: [name]
Statistician:	[name] Dana-Farber Cancer Institute

Agents: Rituximab (commercial supply); Utomilumab (investigational, supplied by Pfizer); PF-04518600 (investigational, supplied by Pfizer); Avelumab (investigational, supplied by Pfizer)

[name] [contact]

IND #: 138620 IND Sponsor: [name]

Protocol Version # / Version Date: Version 11 / 18 February 2021

SCHEMA 1: RELAPSED/REFRACTORY DOSE ESCALATION AND EXPANSION DESIGN

A1a, dose level 1: Rituximab (or rituximab biosimilar) 375mg/m2 IV q7 days x 4 doses, utomilumab 100mg IV q28d, avelumab 3mg/kg IV q14 days; **A1a, dose level 2**: Rituximab (or rituximab biosimilar) 375mg/mg2 IV q7 days x 4 doses, utomilumab 100mg IV q28d, avelumab 10mg/kg IV q14 days; **A2a, dose level 0**: PF-04518600 0.3mg/kg IV q14 days;

A2a, dose level 1: Rituximab (or rituximab biosimilar) 375mg/m2 IV q7 days x 4 doses, PF-04518600 0.3mg/kg IV q14 days;

A2a, dose level 2: Rituximab (or rituximab biosimilar) 375mg/m2 IV q7 days x 4 doses, PF-04518600 0.3mg/kg IV q14 days, utomilumab 100mg IV q28 days;

A3a, dose level 1: Rituximab (or rituximab biosimilar) 375mg/m2 IV q7 days x 4 doses, PF-04518600 0.3mg/kg IV q14 days, avelumab 3mg/kg IV q14 days;

A3a, dose level 2: Rituximab (or rituximab biosimilar) 375mg/m2 IV q7 days x 4 doses, PF-04518600 0.3mg/kg IV q14 days, avelumab 10mg/kg IV q14 days;

RP2D: recommended phase 2 dose (if 0/3 or 1/6 DLTs at dose level 2 for a given cohort, this will be dose level 2; if 2+/6 DLTs at dose level 2 for a given cohort, this will be dose level 1; n=15 patients in total at a given dose)

SCHEMA 2: CRITERIA TO OPEN, AND EARLY STOPPING RULES FOR, PREVIOUSLY UNTREATED COHORTS

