Enrollment will begin with the phase 1 dose escalation stage to test the safety of these combinations in relapsed/refractory FL and to determine the recommended phase 2 dose (RP2D) to use for the phase 1b dose expansion cohorts as well as for the potential upfront cohorts. The cohorts in the phase 1 dose escalation stage will follow a 3+3 dose escalation schema, such that there will be a safety pause and evaluation after the first 3 patients at any given dose level have completed 6 weeks of therapy. If there are no dose limiting toxicities (DLTs) seen, the next dose level will open. If there is 1 DLT, an additional 3 patients will be enrolled at that dose level with a safety pause and evaluation after all 3 have completed 6 weeks of treatment. If there are 2 or more DLTs at any time in a given dose level, no further testing of that dose level will open. The next dose levels will follow the same 3+3 dose escalation schema (**Schema 1**). Once a recommended phase 2 dose is determined, this dose will be used in both the dose expansion cohorts as well as in the potential upfront dosing cohorts.

Enrollment will begin with cohorts A1a, dose level 1, and A2a, dose level 0 in an alternating fashion. Each subsequent cohort will be filled sequentially beginning with cohort A1a dose level 2, followed by cohort A2a dose level 1, then A2a dose level 2, then A3a dose level 1, and finally A3a dose level 2. If a patient is not eligible for the cohort that is being filled preferentially at the time of enrollment due to prior treatment history, they may be enrolled in the next cohort for which they are eligible. Note, if a patient in cohort A2a, dose level 0, has not had a response by the midtreatment response assessment following cycle 3, they will be allowed to received rituximab 375mg/m2 q7d for 4 weeks during cycle 4 (C4D1, C4D8, C4D15, C4D22).

Dose limiting toxicities (DLTs) are defined as any grade 3 or greater toxicity unless directly, and incontrovertibly, related to progressive disease with the exception of the following:

- Grade 3 hematologic abnormalities
- Grade 4 hematologic abnormalities that recover to grade 2 or lower with supportive treatment (including transfusion, IVIg, or growth factor) within 7 days
- Non-hematologic abnormalities:
 - Transient (≤ 24 hours) Grade 3 fatigue, local reactions, or headache that resolves to Grade ≤ 1 ;
 - Grade 3-4 nausea and vomiting controlled by optimal medical therapy within 72 hours;

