Toxicity will be continuously monitored and recorded using CTCAE 4 criteria, up to 30 days following the last dose of the study treatment or until resolution of toxicity to grade 1 or baseline, whichever occurs last. Response will be assessed 4-6 weeks after the completion of therapy (either after cycle 6 of therapy for patients who complete the planned cycles of therapy, or after their last dose of treatment for patients who discontinue treatment before cycle 6) by PET and CT scans of the neck (if involved at baseline), chest, abdomen, and pelvis, as well as at 6, 12, and 18 months from the end of treatment (+/- 2 weeks) in the absence of disease recurrence or progression (PET may be omitted once patient is in CR). In addition, CT scans of the chest, abdomen, and pelvis +/- neck will be obtained 4 weeks (+/- 1 week) after the completion of cycle 3 while on therapy. If patients experience evidence of progressive disease confirmed by imaging while on treatment, they will be allowed to complete treatment if they meet the definition of an indeterminate response according to LyRIC criteria.²

Expected toxicities and potential risks for all drugs are described in Section 6 (Dosing Delays/Dose Modifications). No investigational or commercial agents or therapies other than those described below may be administered with the intent to treat the participant's malignancy.

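### The 94% power and 9% type I error for the Part A rule of at most 3 DLTs in 15 are plain binomial values that ignore selection by the 3+3, and the table entry 0.15 at a 35% rate should be 0.17

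*Combined protocol and SAP*

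**What the plan says.** Section 13.2.1 (Dose Expansion) tests each Part A combination on 15 patients and accepts it as tolerable if no more than three have a DLT. The stated basis is a "null hypothesis for DLT rate of 40% and an alternative hypothesis of 10% with 94% power and a 9% one-sided type I error". The row headed "Prob of observing ≤3 pts with excessive tox" gives 0.99, 0.94, 0.82, 0.65, 0.46, 0.30, 0.15 and 0.09 at true rates of 5, 10, 15, 20, 25, 30, 35 and 40%.

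The same section builds the 15 from the escalation patients plus 9 or 12 new ones: "Whether it is 9 or 12 is dependent on whether 6 or 3 patients were treated at that dose level to determine the RP2D". Schema 1 says how a dose gets there: "if 0/3 or 1/6 DLTs at dose level 2 for a given cohort, this will be dose level 2", and "if 2+/6 DLTs at dose level 2 for a given cohort, this will be dose level 1".

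On timing, section 5.1 says "there will be a safety pause and evaluation after the first 3 patients at any given dose level have completed 6 weeks of therapy". Its DLT definition carries no time limit: "Dose limiting toxicities (DLTs) are defined as any grade 3 or greater toxicity unless directly, and incontrovertibly, related to progressive disease", followed by a list of exceptions. It also says: "Toxicity will be continuously monitored and recorded using CTCAE 4 criteria, up to 30 days following the last dose of the study treatment". It closes a dose level once two or more DLTs have occurred, without restricting when.

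Section 13.2.1 tabulates the 3+3 escalation probabilities separately (0.91 at 10%, 0.31 at 40%) and does not combine them with the 15-patient rule.

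**The concern.** Of the 15 patients tested, 3 or 6 (20% or 40%) were already screened on the outcome being tested: their dose is in expansion because they had few DLTs. A binomial calculation that treats all 15 as fresh describes neither of the two quantities a reader is likely to want. One is the chance that an expanded dose with a given DLT rate is called tolerable. The other is the chance that a dose level passes both the 3+3 and the 15-patient rule. Section 13.2.1 does not say that its figures are neither.

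This matters because the limit of three DLTs, together with at least three complete responses and discussion with regulators, governs whether a combination opens in previously untreated patients. Whoever reviews that step is looking only at a dose that reached expansion.

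The 35% cell is a separate and simpler matter. It does not agree with the calculation that produces every other cell.

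**Working it through.** **Inputs.** Limit of 3 in 15, rates of 10% and 40%, and 12 or 9 added patients (section 13.2.1); a level passes on 0/3 or 1/6 (Schema 1). Patients are taken as independent with one DLT rate p at the level.

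**Step 1: the plan's own figures.** P(X ≤ 3), X ~ Binomial(15, p):

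| p | 0.05 | 0.10 | 0.15 | 0.20 | 0.25 | 0.30 | 0.35 | 0.40 |
|---|---|---|---|---|---|---|---|---|
| Printed | 0.99 | 0.94 | 0.82 | 0.65 | 0.46 | 0.30 | 0.15 | 0.09 |
| Computed | 0.9945 | 0.9444 | 0.8227 | 0.6482 | 0.4613 | 0.2969 | 0.1727 | 0.0905 |

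Seven cells agree and the 35% cell does not. Neighbouring variants do not give 0.15 either: ≤3 of 14 is 0.22, ≤3 of 16 is 0.13, and ≤2 of 15 is 0.06.

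**Step 2: passing the 3+3, all DLTs seen at the decision.** P(pass) = (1−p)³ + 3p(1−p)² × (1−p)³.
- 40%: 0.216 + 0.432 × 0.216 = 0.216 + 0.0933 = 0.3093
- 10%: 0.729 + 0.243 × 0.729 = 0.729 + 0.1771 = 0.9061

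These match the plan's escalation table (0.31 and 0.91), so that table makes the same timing assumption.

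**Step 3: passing the 3+3 and then ≤3 in 15, one level (joint).** After 0/3, at most 3 of 12 new patients may have a DLT; after 1/6, at most 2 of 9.
- 40%: 0.216 × 0.2253 + 0.0933 × 0.2318 = 0.0487 + 0.0216 = 0.0703
- 10%: 0.729 × 0.9744 + 0.1771 × 0.9470 = 0.7103 + 0.1678 = 0.8781

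**Step 4: given that the dose reached expansion (conditional).**
- 40%: 0.0703 / 0.3093 = 0.227
- 10%: 0.8781 / 0.9061 = 0.969

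| p | 0.10 | 0.20 | 0.30 | 0.35 | 0.40 |
|---|---|---|---|---|---|
| Plain binomial | 0.94 | 0.65 | 0.30 | 0.17 | 0.09 |
| Conditional on passing the 3+3 | 0.97 | 0.78 | 0.48 | 0.34 | 0.23 |
| Joint, one level | 0.88 | 0.55 | 0.24 | 0.14 | 0.07 |

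A simulation of 300,000 runs per rate gave the same conditional and joint values at 10% and 40%.

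**Step 5: if some DLTs come after the decision.** The share is an assumption, and there are two readings of what a late DLT in an escalation patient does.
- *It counts only towards the 15.* With half of DLTs early, the conditional value at 40% is 0.12 and the joint value at 10% is 0.93. As the early share goes to zero, both rows reach the plain binomial values.
- *It can also close the level.* With almost none early, a level survives if at most 1 of 3 escalation patients has a DLT. At 40% the joint value is 0.216 × 0.2253 + 0.432 × 0.0834 = 0.0847, and the conditional value is 0.0847 / 0.648 = 0.13. At 10% the joint value is 0.729 × 0.9744 + 0.243 × 0.8891 = 0.93. With half early, the conditional value at 40% is 0.16 and the joint value at 10% is 0.90.

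On both readings later DLTs move the rows towards the plain binomial values, and the joint value at 40% stays at or below 0.0905.

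**The case against.** The strongest reply is that nothing in the 94%/9% pair is miscalculated. The row is presented as a probability at a true but unknown rate, which is the usual fixed-rate convention. The make-up of the 15 and the 3+3 pass probabilities are disclosed in the same section. This stands as far as it goes: apart from the 35% cell, the fault is an unlabelled quantity, not a wrong sum.

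A reader might infer that the true type I error is 23%, or that the design lets too many toxic combinations through. The documents do not support that. The 23% applies only to doses that have already passed a screen which, by the plan's own table, a 40%-rate dose passes 31% of the time. With that screen counted, false acceptance at one level is 7%, below the printed 9%.

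A reader might also take 88% as the power of the whole procedure, including the Schema 1 fallback to dose level 1. That would need DLT rates at both levels, which the documents do not give. If level 1 were at 5% and level 2 at 10% (an assumption), with all DLTs early, the chance that some level is expanded and called tolerable is 0.9734 × 0.8781 + 0.0939 × 0.9706 = 0.946, close to the printed 94%. In cohort A2, moreover, level 1 lacks utomilumab, so the fallback there is not the same combination.

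Finally, the size of the effect depends on DLT timing. This also stands. It is why the added rows should be presented as one stated case and not as a settled property of the design.

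**Conclusion.** Both parts hold. The 35% entry is wrong by the plan's own method and should read 0.17. It affects neither the 94%/9% pair nor the decision limit.

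The pair itself is correct for 15 unselected patients but ignores that 3 or 6 of them have already passed the 3+3. When all DLTs are seen at the 3+3 decision, the error rate at 40% for an expanded dose is 23%, not 9%, and single-level power at 10% is 88%, not 94%. Overall false acceptance at one level is not inflated (7%).

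This rests on independent patients, one DLT rate at the level, the same DLT definition in escalation and expansion, and the timing assumption built into the plan's escalation table. The documents settle neither the share of DLTs that arise before the decision nor whether late DLTs in escalation patients also close a level. The DLT definition is open-ended, treatment runs for six 28-day cycles (section 5.2), and section 6.1 warns that immune-related events may appear only after several weeks. If few DLTs are early, the discrepancy shrinks; on the reading that late DLTs only count towards the 15, it vanishes in the limit.

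**What to change.** In section 13.2.1:

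1. Change the 35% entry from 0.15 to 0.17.
2. Label the row and the 94%/9% pair as plain binomial values for 15 patients that ignore selection by the 3+3.
3. Add two rows at 10, 20, 30, 35 and 40%: conditional on passing the 3+3 (0.97, 0.78, 0.48, 0.34, 0.23), and joint with the 3+3 at one dose level (0.88, 0.55, 0.24, 0.14, 0.07). Mark both as the case where all DLTs are seen at the 3+3 decision, the assumption already used in the escalation table, and state that later DLTs move both rows towards the plain binomial values.

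Figures for intermediate shares of early DLTs, and totals over two levels with fallback, should not be written in as properties of the design, because they need inputs the documents do not give.

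The cost is one table cell, two rows and a few sentences. The decision limit, stopping rules and sample size stay as they are.
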